5. Time to transformation into AML
6. Overall survival
7. Safety profile

VII. CRITERIA FOR WITHDRAWAL

Reasons for withdrawal include:

- Withdrawal of consent or the subject refuses to continue treatment and/or procedures/observations.
- Relapse/progression unless the treating physician determines that the patient has achieved clinical benefit, at which time further therapy on protocol may be permitted with approval from the PI and the discussion documented in the patient's medical record.
- No response after at least 6 courses unless the treating physician determines that the patient has achieved clinical benefit, at which time further therapy on protocol may be permitted with approval from the PI and the discussion documented in the medical record.
 - Intercurrent illness preventing further administration of protocol treatment,
 - Unacceptable toxicity that in the opinion of the investigator makes continued therapy unsafe.

VIII. CRITERIA FOR RESPONSE

The response criteria recommended by the MDS International Working Group.

Definitions:

Complete Response (CR):

Normalization of the peripheral blood and bone marrow with <5% bone marrow blasts, a peripheral blood granulocyte count $> (1.0 \times 10^9/L)$, and a platelet count $> 100 \times 10^9/L$.

Partial response (PR):

As above except for the presence of 6-15% marrow blasts, or 50% reduction if <15% at start of treatment.

Marrow CR:

Blasts \leq 5% and decrease by \geq 50% from baseline (baseline blasts should be above 5% to be eligible for marrow CR)

Hematologic Improvement (HI):

Platelets increase by 50% and to above $30 \times 10^9/L$ untransfused (if lower than that pretherapy); or granulocytes increase by 100% and to above $10^9/L$ (if lower than that pretherapy); or hemoglobin increase by 2 g/dl; or transfusion independent; or splenomegaly reduction by $> 50\%$; or monocytosis reduction by $> 50\%$ if pretreatment $> 5 \times 10^9/L$.

IX. REPORTING REQUIREMENTS

All adverse and serious adverse events will be recorded and reported according to the Department of Leukemia guidelines (appendix C)

X. Randomization

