The Department of Biostatistics will provide and maintain a website ("Clinical Trial Conduct": <https://biostatistics.mdanderson.org/ClinicalTrialConduct/>) for patients enrolled on this study. The Clinical Trial Conduct website resides on a secure server, and access is gained through usernames and passwords provided to personnel responsible for enrolling patients and updating patient data. The website is accessed through a browser using secure socket layer (SSL) technology. Personnel responsible for enrolling patients on trials, which includes the principal investigator(s), research nurse(s), and data coordinator(s), will be trained by members of the Department of Biostatistics in the use of the trial website; the importance of timely updating of follow-up times and recording of events will be emphasized in training.

XI. Data Safety Monitoring

A data safety monitoring board (DSMB) at MD Anderson will monitor the trial for the safety.

XII. STATISTICAL CONSIDERATIONS

General Description

This is a Phase II open-label, efficacy and toxicity study of two treatment arms (lower doses of Decitabine versus Azacitidine) in subjects with low risk or intermediate-1 myelodysplastic syndrome. Patients will be enrolled to evaluate the 2 agents. In arm A, Decitabine (DAC) will be administered 20mg/m² IV daily for 3 days every 28 days and in treatment B Azacitidine (AZA) will be administered 75mg/m² SC or IV daily for 3 days every 28 days. For both arms, one course will be considered of 4 weeks. An adaptive randomization design will be employed to compare the efficacy between the two arms. The primary efficacy outcome is the overall improvement rate (OIR), defined as complete remission (CR), partial remission (PR), marrow CR (mCR), or hematologic improvement (HI), assessed after maximum of 2 cycles. At the end of the trial, we will estimate the probability that one arm is superior to the other. We will also evaluate toxicity on each arm. A maximum of 120 patients will be accrued, at an expected accrual rate of 3 patients per month.

Study design

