Evidence of Toxicity will be monitored closely in all patients. For each arm, treatment will be terminated if $\Pr(\text{non hematological grade 3 or higher Toxicity} > 0.2 | \text{data}) > 0.95$, and the toxicity rate is assumed to follow a non-informative prior of $\text{Beta}(0.4, 1.6)$. Table 1 shows the simulation of the trial. The treatment will be stopped if the number of patients with study drug related toxicities equal to or greater than indicated (i.e., #pts with tox) among the number of patients accrued (i.e., #pts): 4/5, 5/10, 7/15, 8/20, 9/25, 11/30, 12/35, 13/40, 15/45, 16/50, 17/55, 18/60, 19/65, 21/70, 22/75, 23/80, 24/85, 26/90, 27/95, 28/100, 29/105, 30/110, 31/115, 33/120.

Table 1: Operating characteristics of Safety Monitoring (based on 10000 simulations)

True probability	Stop probability	Average sample size
0.15	0.02	117.7
0.2	0.15	108.1
0.25	0.51	83.3
0.3	0.87	53

Table 2: Operating characteristics of adaptive randomization design to compare DAC with AZA. Randomly assign 20 patients to each arm with equal probability before adapting the randomization, tuning parameter of 0.5, and accrual rate of 3 patients/month.

	Arm A	Arm B
OIR Rate	0.05	0.1
Expected # of Patients	20.8	20.9
Pr(Select)	0.03	0.23

Pr(Select Early)	0.01	0.11
Pr(Stop Early)	0.85	0.51
OIR Rate	0.1	0.23
Expected # of Patients	25.5	28.7
Pr(Select)	0.02	0.52
Pr(Select Early)	0.01	0.38
Pr(Stop Early)	0.86	0.13
OIR Rate	0.2	0.4
Expected # of Patients	28.9	35.9
Pr(Select)	0.01	0.86
Pr(Select Early)	0.01	0.81
Pr(Stop Early)	0.85	0.01
OIR Rate	0.23	0.23
Expected # of Patients	44.3	44
Pr(Select)	0.17	0.18
Pr(Select Early)	0.13	0.13
Pr(Stop Early)	0.26	0.24
OIR Rate	0.3	0.5
Expected # of Patients	30.7	38.6
Pr(Select)	0.01	0.85
Pr(Select Early)	0.01	0.81
Pr(Stop Early)	0.81	0.01

Analysis Plan

Data analysis will be performed using SAS or S-plus, as appropriate. All patients will be included in the intent-to-treat analysis for efficacy. Demographic and disease characteristics of the patients at registration will be summarized using descriptive statistics such as mean, standard deviation (SD), median and range. The OIR for both arms will be estimated by Bayesian posterior estimates, along with the 95% credible intervals. The posterior probability that one treatment is better than the other will be computed, and the 95% credible interval of the posterior probability will also be estimated. Time to event end points, such as response duration, overall survival and

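### The toxicity boundaries divide by patients accrued, with no follow-up period, so Table 1 does not describe how the rule as written performs

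*Combined protocol and SAP*

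**What the plan says.** Section XII, Toxicity Monitoring, terminates treatment in an arm when the posterior probability that the rate of grade 3 or higher non-hematological toxicity exceeds 0.2 is above 0.95. The prior is Beta(0.4, 1.6): "the toxicity rate is assumed to follow a non-informative prior of" that form. In practice the rule is a list of counts. The numerator is "the number of patients with study drug related toxicities equal to or greater than indicated". The denominator is given by "among the number of patients accrued (i.e., #pts): 4/5, 5/10, 7/15, 8/20", and the list ends "28/100, 29/105, 30/110, 31/115, 33/120". Neither part carries a cycle number, a day range or a minimum follow-up, and no pause in enrolment is described.

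Table 1 is titled "Operating characteristics of Safety Monitoring (based on 10000 simulations". It states no accrual rate, whereas Table 2 does.

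Three other places matter:
- Section XII, General Description: "A maximum of 120 patients will be accrued, at an expected accrual rate of 3 patients per month". The same section assesses the efficacy outcome after at most 2 cycles, and the adaptive comparison uses patients with evaluable response.
- Section VII, Criteria for Withdrawal, lists as one reason: "No response after at least 6 courses unless the treating physician determines that the patient has achieved clinical benefit". No maximum number of cycles is given.
- Section VI, After Cycle 3, has visits continuing for as long as the patient stays on study.

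**The concern.** A patient enrolled last week adds one to the denominator and can hardly have added to the numerator. The observed proportion at each check is therefore biased downward, most of all at the first checks, when the boundary is meant to protect the next patients. The efficacy rule in the same section avoids this by having an assessment window and an evaluable set.

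The 20% limit also lacks a time frame. It could mean toxicity within some early period or at any time on treatment. Under open-ended treatment these are different quantities, and two teams could apply the rule differently to the same data.

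At stake are how many patients are treated in an arm that is too toxic, and whether Table 1 can be relied on as a description of that protection.

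**Working it through.** **Step 1: the boundaries.** With x toxicities in n patients the posterior is Beta(0.4 + x, 1.6 + n − x). The boundary is the smallest x with Pr(rate > 0.2) > 0.95.
- n = 5: x = 3 gives 0.948 and x = 4 gives 0.993, so 4/5.
- n = 10: x = 4 gives 0.895 and x = 5 gives 0.971, so 5/10.
- n = 20: x = 7 gives 0.923 and x = 8 gives 0.972, so 8/20.

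Of the 24 printed counts, 19 match. At n = 45, 70, 90, 95 and 120 the printed count is one higher than the rule gives. That is a separate matter and does not affect checks up to n = 40.

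**Step 2: Table 1.** An exact binomial recursion over the 24 printed counts was run with checks every 5 patients to 120 and every outcome known at the check.

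| True rate | Stop: stated | Stop: recomputed | Average N: stated | Average N: recomputed |
|---|---|---|---|---|
| 0.15 | 0.02 | 0.024 | 117.7 | 117.7 |
| 0.20 | 0.15 | 0.151 | 108.1 | 108.1 |
| 0.25 | 0.51 | 0.517 (0.513 if a crossing at 120 is not counted) | 83.3 | 83.3 |
| 0.30 | 0.87 | 0.872 (0.867) | 53 | 53.0 |

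The match shows that Table 1 contains no delay between accrual and outcome.

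**Step 3: how much is unseen at the first check.** Three patients per month over two arms is 1.5 per arm per month, a mean gap of 0.67 months. With even spacing, the first five patients have been followed 2.67, 2.00, 1.33, 0.67 and 0 months when the fifth enters. Two 28-day cycles are 56/30.44 = 1.84 months. The mean share of that window observed is (1 + 1 + 0.72 + 0.36 + 0)/5 = 0.62. For 6 cycles (5.52 months) it is (0.48 + 0.36 + 0.24 + 0.12 + 0)/5 = 0.24.

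**Step 4: effect on stopping.** Assumptions, none of them from the documents except the accrual rate and the counts:
- 1.5 patients per arm per month with random arrivals.
- At most 40 per arm (Table 2 expects 20.8 to 44.3).
- A check as each fifth patient enters.
- Toxicity times uniform over 2 or 6 cycles.

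The immediate-outcome row is exact; the others are simulated. Ranges show the spread between independent runs.

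| Rule | True 30%: stop (treated) | True 20%: stop |
|---|---|---|
| Immediate outcomes | 0.52 (30.5) | 0.10 |
| Accrued, 2 cycles | 0.40–0.41 (34) | 0.05–0.06 |
| Accrued, 6 cycles | 0.27–0.28 (37) | 0.02–0.03 |
| Completers only, 2 cycles | 0.49–0.50 (31) | 0.09–0.10 |
| Completers only, 6 cycles | 0.42–0.43 (34) | 0.09 |

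The moment of the check matters. If each check is placed just before the next patient enters, the accrued rule at 30% gives 0.45 (33 treated) for 2 cycles and 0.34 (36 treated) for 6. The direction is unchanged.

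**Step 5: on Table 1's own scale.** With up to 120 in the arm, a true rate of 30%, toxicity over 2 cycles and 1.5 per month, the accrued rule stops with probability 0.83 to 0.86 and average N 58 to 63, depending on the moment of the check. The stated figures are 0.87 and 53. With toxicity spread over 6 or 12 months, average N is 70.5 or 83.2.

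**The case against.** The strongest reply is that on the scale Table 1 uses, a 2-cycle lag costs about 5 to 10 patients and barely changes the stop probability, and that larger effects depend on timing the documents do not give. That stands, and the size should be read with it. The smaller samples that Table 2 expects make the loss larger, and the mismatch between the rule and its table does not depend on timing.

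It can also be said that other safeguards exist: toxicity is to be watched closely in all patients, a DSMB monitors safety (Section XI), and unacceptable toxicity is a reason for withdrawal. These help, but they do not define this rule.

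A reader might go further and infer that, because toxicity accumulates over long treatment, an arm would be wrongly stopped late, and the better arm most of all. The documents do not support that. Suppose a constant hazard gives 10% over 2 cycles, with 23% of patients treated for 24 cycles and the rest for 6. An uncapped count stops that arm with probability about 0.42, and a 2-cycle count with about 0.001. But the share who ever have a toxicity is 0.23 × (1 − 0.9^12) + 0.77 × (1 − 0.9^3) = 0.23 × 0.718 + 0.77 × 0.271 = 0.37. If the 20% limit means any time on treatment, stopping is not an error. Nothing says that it means 2 cycles, and no figure in the documents shows the better arm to be more exposed.

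Nor does the plan say that monitoring ends with accrual. The printed counts end at 120, but the posterior criterion is not confined to the accrual period.

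**Conclusion.** The concern holds in this form: the rule as written counts unfollowed patients as toxicity-free, gives its 20% limit no period, and is described by a table that assumes immediate outcomes. The arm-stopping protection is weaker than stated.

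In the 40-per-arm illustration at a true 30%, the stop probability falls by about 0.11 (2 cycles) or 0.25 (6 cycles), with about 3 to 6 more patients treated. At up to 120 per arm with a 2-cycle lag the loss is 0.01 to 0.04 in stop probability and 5 to 10 patients. All these sizes rest on assumed toxicity timing. Whether late accumulation makes the rule too strict cannot be judged until the sponsor says what period the limit covers.

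**What to change.** In Section XII, Toxicity Monitoring:

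1. State the period over which a patient is assessed for toxicity. The choice is the sponsor's. State also whether the 20% limit refers to that period or to any time on treatment, and reconcile this with open-ended treatment.
2. Redefine the denominator from patients accrued to patients followed for the full period, and count toxicities in those same patients over that same period. Patients with toxicity should not enter earlier than those without. A denominator of patients who completed the period or already had the event over-counts toxicity: in the illustration it stops with probability about 0.61 at a true 30% over 6 cycles, above the 0.52 with full information, and about 0.19 at a true 20%.
3. Say how patients who leave before the period ends are counted.
4. Rerun Table 1 with the accrual rate and the new denominator. The 0.2 limit and the 0.95 cut-off need not change for this.
5. Report toxicity after the period to the DSMB, by arm, so that it is not lost.

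The cost is a few sentences and one simulation. At a true 20% rate, stops rise from about 0.06 to about 0.10 (completers, 2 cycles, 40 per arm), in line with immediate outcomes. Completers only does not recover everything when toxicity is late (0.43 with 34 treated over 6 cycles), because enrolment continues while outcomes are pending.

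This version is marked closed to new entry, so the change bears on patients still on treatment, on how the safety monitoring is reported, and on any reuse of the design.

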Patients will be assigned to receive Decitabine or Azacitidine, using an adaptive procedure that bases assignment probabilities on observed results in preceding patients. At first, 20 patients will be assigned to each arm with equal probability. As efficacy data accrues, patient assignment to the two arms will become unbalanced in favor of the one that has the higher overall improvement rate (OIR). The OIR for both arms will be estimated with a 95% CI (similar to Bayesian highest posterior density interval).

Based on previous studies, we expect an OIR of about 23% in both arms. Therefore, we assume OIR has a prior Beta distribution (0.46, 1.54) with mean 0.23. Let OIRa and OIRb denote the overall improvement rates for arm A and arm B, respectively. Beginning with the 21st patient in each arm and for each subsequent patient, we will compare OIRa with OIRb, incorporating data from all patients with evaluable response. In order to avoid favoring one arm earlier in a large trial, instead of assigning patients with posterior probability ($P_a = \Pr(\text{OIR}_a > \text{OIR}_b | \text{data})$ and $P_b = 1 - P_a$), we use the following formula to assign patients:

$$A_a = \frac{\sqrt{P_a}}{\sqrt{P_a} + \sqrt{P_b}}, \quad A_b = 1 - A_a, \text{ where } A_a \text{ is the probability of assigning patients to arm A,}$$

A_b is the probability of assigning patients to arm B, P_a is the posterior probability that arm A is superior to arm B and P_b is the posterior probability that arm B is superior to arm A.

If at any point during the trial $\Pr(\text{OIR}_A > \text{OIR}_B | \text{data}) > 0.95$ (or < 0.05) the schedule A (or B) will be selected as superior. If accruing information gives strong evidence that an OIR of 23% or greater is unlikely to be true for any one of the treatment arms ($\Pr(\text{OIR}_A \text{ or } \text{OIR}_B > 0.23 | \text{data}) < 0.05$), assignment to that arm will be stopped. If the maximum of 120 patients is enrolled and evaluated and $\Pr(\text{OIR}_A > \text{OIR}_B | \text{data}) > 0.9$ (or < 0.1), we will declare that arm A (or B) has a higher OIR rate than arm B (or A). Otherwise, the trial will be inconclusive. We used simulation (5,000 simulations per scenario) to evaluate the performance of the adaptive randomization procedure under several different scenarios (Table 2). There was an 86% power to select a superior arm (arm B) if the OIR rates are 20% and 40%, respectively.

Toxicity Monitoring

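### The 95% credible interval planned for the probability that one arm is better has zero width under the fixed Beta priors; an interval for the OIR difference should replace it (minor)

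*Combined protocol and SAP*

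**What the plan says.** All the relevant text is in section XII of the combined protocol and SAP.

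- **General Description** names the end-of-trial result: "At the end of the trial, we will estimate the probability that one arm is superior to the other".
- **Study design** sets the prior: "we assume OIR has a prior Beta distribution (0.46, 1.54) with mean 0.23". It defines P_a, which "is the posterior probability that arm A is superior to arm B", and uses it for allocation, for early selection (0.95 or 0.05) and for the final declaration (0.9 or 0.1). It also plans a 95% interval for the OIR of each arm.
- **Analysis Plan** repeats the per-arm intervals: "The OIR for both arms will be estimated by Bayesian posterior estimates, along with the 95% credible intervals". It then plans the posterior probability that one treatment is better and adds that "the 95% credible interval of the posterior probability will also be estimated".

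No section names a difference, ratio or odds ratio of OIR. The log-rank and Cox analyses of the time-to-event endpoints carry no stated interval.

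**The concern.** A credible interval describes a quantity that is still uncertain once the data are in, such as an arm's OIR or the difference between two OIRs. The probability that one OIR exceeds the other is not such a quantity. It is obtained by averaging over the uncertainty in both OIRs, so with fixed priors and observed counts nothing about it is left to vary.

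The primary objective is to compare response rates. If the only interval stated for that comparison carries no information, the report would give a probability of superiority with no effect size and no valid measure of precision beside it. An analyst who tries to follow the clause might also fill it with simulation error. A reader could then take a very narrow interval around, say, 0.95 as a sign of a precise comparison.

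**Working it through.** **Figure in the plan.** The plan states no value for this interval, so there is none to reproduce. The nearest stated figure, 86% power at OIR 20% vs 40%, does not depend on it. For orientation, 1,500 simulated trials gave 0.852. They assumed a 2-month outcome delay, monitoring from the 41st patient, accrual ending when an arm is dropped, and pending outcomes counted at the end. Other readings of the unstated settings gave 0.85 to 0.92.

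**Inputs.** The Beta(0.46, 1.54) prior for each arm comes from Study design. The plan gives no results, so all counts below are hypothetical.

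**Step 1: posteriors.** With x responders among n patients, the posterior is Beta(0.46 + x, 1.54 + n - x).

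- Case 1, A 4/20 and B 9/20: Beta(4.46, 17.54) and Beta(9.46, 12.54).
- Case 2, A 11/60 and B 19/60: Beta(11.46, 50.54) and Beta(19.46, 42.54).

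**Step 2: probability of superiority.** Pr(B > A | data) = ∫ F_A(t) f_B(t) dt over 0 to 1, where F_A is the posterior distribution function of OIR_A and f_B the posterior density of OIR_B. Both are fully determined by the prior and the counts, so the integral is one number: 0.95365 in case 1 and 0.95434 in case 2. Its credible interval runs from that value to the same value. A distribution for it would need uncertainty about the prior parameters (a hyperprior) or a set of priors, and the plan has neither.

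**Step 3: what a non-zero width would measure.** If the probability were estimated from M posterior draws, its simulation-error interval would be Pr ± 1.96·√(Pr(1 − Pr)/M).

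| Draws M | Case 1 | Case 2 |
|---|---|---|
| 1,000 | 0.941 to 0.967 | 0.941 to 0.967 |
| 10,000 | 0.950 to 0.958 | 0.950 to 0.958 |
| 1,000,000 | 0.9532 to 0.9541 | 0.9539 to 0.9548 |

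The width falls from 0.026 to 0.0008, a factor of √1,000 ≈ 32, with no change in the patients. At a given M it is about the same for 40 patients as for 120.

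**Step 4: an interval that does describe the comparison.** Median and 2.5% and 97.5% quantiles of OIR_B - OIR_A, from 4,000,000 draws of the same posteriors:

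- Case 1: 0.229 (-0.039 to 0.482), width 0.521.
- Case 2: 0.129 (-0.021 to 0.278), width 0.299.

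The ratio of widths is 0.521/0.299 = 1.74, while the two probabilities agree to three decimals.

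**Step 5: how much is lost.** A reader can combine the planned per-arm outputs: difference of posterior means ± √(h_A² + h_B²), where h is half the width of each arm's 95% interval.

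- Case 1: the intervals are 0.067 to 0.389 and 0.236 to 0.636, so h is 0.161 and 0.200. The means are 4.46/22 = 0.203 and 9.46/22 = 0.430. Result: 0.227 ± 0.257, or -0.030 to 0.484. Largest error 0.009.
- Case 2: the intervals are 0.099 to 0.290 and 0.205 to 0.434. Result: 0.129 ± 0.149, or -0.020 to 0.278. Largest error 0.002.
- Sparser or unequal counts do less well: largest error 0.015 for 2/20 vs 10/40, 0.015 for 3/20 vs 12/40, and 0.018 for 1/20 vs 3/20 (where arm A would already meet the futility rule).

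In the cases checked, the approximation is good to about 0.02.

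**The case against.** The strongest reply is that nothing turns on the clause. Every rule in Study design uses the point value of a posterior probability, and the per-arm posteriors follow from the counts, so any contrast can be recovered. That is correct, and it caps the severity at minor. It does not make the clause informative.

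Three further objections have force:

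- The Monte Carlo figures measure no planned analysis. The plan does not say that the probability will be found by posterior draws; the simulations it mentions are for operating characteristics. Step 3 shows only what would happen if someone filled the clause that way.
- Case 2 is an unlikely trial. Allocation favours the better arm, and a probability above 0.95 selects it during the trial. In 1,500 simulated trials (500 each at OIR 0.23/0.23, 0.2/0.3 and 0.2/0.4; immediate outcomes, monitoring from the 41st patient, trial ending when an arm closes), one reached 120 patients with Pr(B > A) above 0.95. The case shows that equal probabilities can go with unequal precision, and no more.
- The document does not name the OIR difference as the target. The clause may be a slip for an interval on that difference, but the text does not settle it, and deleting the clause would also remove the error.

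A reader might infer more than the text supports. One could say that the interval is undefined, but a point mass does have an interval, of zero width, so degenerate is the accurate word. One could say that it is the only interval for any between-arm comparison. That is safe only for OIR, because a Cox hazard ratio would normally be reported with an interval even though none is stated.

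**Conclusion.** The point holds as a minor error in the reporting plan. Under the fixed Beta priors, the credible interval planned for the probability of superiority has zero width and tells the reader nothing about the precision of the comparison, and no other interval is stated for the between-arm OIR comparison. In the two illustrations the same probability, 0.954, goes with difference intervals of width 0.52 and 0.30.

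This rests on the prior parameters being fixed, as Study design states, and on hypothetical counts for the sizes.

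A reader might be tempted to conclude that the Bayesian comparison itself, the stopping rules or the 86% power are unsound. The documents do not support that. The posterior probability and the per-arm intervals are valid, and no randomization, stopping or selection rule, power figure or entry in Table 2 of section XII uses the interval in question.

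**What to change.** In the Analysis Plan of section XII, delete the clause on the interval of the posterior probability. In its place, state that the posterior median and 95% credible interval of the OIR difference, OIR_B - OIR_A, will be reported with it. Keep the posterior probability and the per-arm OIR estimates and intervals as planned, and state the direction of the difference so that its sign agrees with the probability reported.

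The cost is one clause. The difference comes from the same two Beta posteriors and needs no new data, no new assumption and no new simulation of the design. Deletion alone would also cure the error, but it would leave the primary comparison without a stated effect size or interval.
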